### 8.2. Adverse Events

#### 8.2.1. Adverse Event Definitions

A TEAE is any AE either reported for the first time or worsening of a pre-existing event after first dose of study drug. Analysis of AEs (as discussed below) will be limited to TEAEs, but data listings will include all AEs regardless of their timing in relation to study drug administration.

Adverse events will be tabulated by MedDRA PT and SOC. Severity of AEs will be graded using the National Cancer Institute CTCAE. The CTCAE version 4.03 is used for this study. The CTCAE reporting guidelines and grading details are available on the Cancer Therapy Evaluation Program website.

The subset of AEs considered by the investigator to be related to study drug will be considered to be treatment-related AEs. If the investigator does not specify the relationship of the AE to study drug, the AE will be considered to be treatment-related. The incidence, frequency, duration, and severity of AEs and treatment-related AEs will be tabulated. In addition, SAEs will also be tabulated.

A grading (severity) scale is provided for each AE term. If the toxicity is not included in the CTCAE v4.03 criteria, it will be rated on a scale of 1 to 4 as follows: 1 = mild, 2 = moderate, 3 = severe, and 4 = life threatening. All toxicities will be graded based on the worst level reached, not the level they may have reached if they had not been treated. When the intensity of an AE changes over time for a reporting period (eg, between visits), each change in intensity will be collected as an AE until the event resolves. Only the worst grade will be reported in AE summaries. Also, the Grade 3 or higher AEs will be reported in a listing.

Any missing onset date, causality, or severity must be queried for resolution. Unresolved missing causality and severity will be handled according to the following rules:

- An unresolved missing causality will be considered treatment-related.
- An unresolved missing severity will be identified as an unknown severity.

For purposes of analysis, all AEs will be considered TEAEs unless the AE can unequivocally be defined as not treatment-emergent.

## **8.2.2.** Dose-Limiting Toxicities

The number of subjects with DLTs and the type of DLT will be listed by dose level and dose administration schedule. If a dose with multiple schedules is tested, the DLTs will be summarized by dose and by schedules.

#### **8.2.3. Maximum Tolerated Dose**

- In Part 1 of the study, the MTD will be defined as 1 dose level below that at which ≥ one-third of subjects in a particular cohort have DLTs.
- In Part 2 of the study, toxicities will continue to be monitored. If the cumulative incidence of DLTs occurs in ≥ 33% of subjects after 6 subjects have been observed for at least 28 days, further enrollment may be interrupted, and the investigators and sponsor will meet and reassess the MTD. All AEs, regardless of the time of occurrence on study, may be considered in DLT determination purposes.

#### 8.2.4. Immune-Related Adverse Events

The number of subjects with irAEs and type of irAE will be listed by dose level and dose administration schedule for the Part 1 FAS population and by tumor type in the Part 1 Safety Expansion and Part 2 FAS population. Adverse event terms will be reviewed periodically without respect to treatment group by the medical monitor and clinical scientist to determine which AE terms correspond to irAEs. This periodic review may also occur after database lock. The medical monitor and clinical scientist will also review investigator reported AEs to determine if they qualify as irAEs. For example, a rash will be counted as an irAE even if the investigator did not report it as an irAE.

#### **8.2.5.** Adverse Event Summaries

An overall summary of AEs by treatment group and by tumor type as applicable will include the following:

- Number (%) of subjects reporting any TEAEs
- Number (%) of subjects reporting any DLTs
- Number (%) of subjects reporting any SAEs
- Number (%) of subjects reporting any Grade 3 or higher TEAEs
- Number (%) of subjects reporting any TEAEs related to INCAGN01876
- Number (%) of subjects who dose interrupted INCAGN01876 because of TEAEs
- Number (%) of subjects who permanently discontinued INCAGN01876 because of TEAEs
- Number (%) of subjects with INCAGN01876 dose reductions because of TEAEs
- Number (%) of subjects who had a fatal TEAE
- Number (%) of subjects who withdrew from study because of an TEAE

The following summaries will be produced by MedDRA term (if 10 or fewer subjects appear in a table, a listing may be appropriate):

- Summary of TEAEs by SOC and PT
- Summary of TEAEs by PT in decreasing order of frequency
- Summary of TEAEs by SOC, PT, and highest CTCAE grade/maximum severity
- Summary of Grade 3 or higher TEAEs by SOC and PT
- Summary of INCAGN01876 treatment-related AEs by SOC and PT
- Summary of Grade 3 or higher INCAGN01876 treatment-related AEs by SOC and PT
- Summary of all TEAEs, treatment-related AEs, Grade 3 or 4 TEAEs, and treatment-related Grade 3 or 4 TEAEs.
- Summary of INCAGN01876 treatment-related AEs by SOC, PT, and highest CTCAE grade/maximum severity
- Summary of TEAEs leading to death by SOC and PT
- Summary of treatment-emergent SAEs by SOC and PT
- Summary of treatment-emergent SAEs by PT in descending order of frequency
- Summary of INCAGN01876 treatment-related SAEs by SOC and PT
- Summary of TEAEs leading to INCAGN01876 dose reduction by SOC and PT
- Summary of TEAEs leading to INCAGN01876 dose interruption by SOC and PT
- Summary of TEAEs leading to discontinuation of INCAGN01876 by SOC and PT
- Summary of treatment-emergent non-SAE by SOC and PT.

- Summary of irAEs by SOC and PT.
- Summary of Grade 3 or higher irAEs by SOC and PT.
- Number (%) of subjects reporting an immune-related AE (irAE)
- Number (%) of subjects reporting any Grade 3 or 4 irAE
- Number (%) of subjects reporting an immune-related treatment-related AE (irAE)
- Number (%) of subjects reporting an immune-related treatment-related Grade 3 or 4 AE (irAE)

A KM analysis of time to first TEAE of Grade 3 or higher will be conducted. A KM analysis of time to first treatment-related irAE of Grade 3 or higher will be conducted.

## **8.3.** Clinical Laboratory Tests

#### **8.3.1.** Laboratory Value Definitions

Laboratory values and change from baseline values will be summarized descriptively by visit. Baseline will be determined according to Section 4.1.3. If there are multiple values that meet the criteria for baseline, additional rules may be provided after consultation with the medical monitor to delineate which value will be defined as baseline.

Laboratory test values outside the normal range will be assessed for severity based on CTCAE grade or similar criteria where clinical intervention is required for CTCAE grading. The incidence of abnormal laboratory values and shift tables relative to baseline will be tabulated.

### **8.3.2.** Laboratory Value Summaries

Laboratory values and change from baseline values will be summarized descriptively by visit. The baseline value will be determined using the nonmissing values collected before the first dose, prioritizing scheduled assessments for baseline identification over unscheduled visits. The last record before administration in the highest priority will be considered the baseline record. For baseline laboratory candidates with the same date and time in the same priority category, additional rules may be provided after consultation with the medical monitor to delineate which value will be defined as baseline.

All tests with numeric values will have a unique unit per test. Any laboratory test results and associated normal ranges from local laboratories will be converted to SI units. For the limited number of cases where the associated normal ranges from a local laboratory cannot be obtained despite due diligence, if query is unsuccessful at resolving issue and analysis is mandatory then the clinical scientist and medical monitor can provide a suitable normal range to be used in determining CTC grading and flags for above and below normal.

When there are multiple laboratory nonmissing values for a subject's particular test at a scheduled visit, the laboratory value with the smallest laboratory sequence number will be used in by-visit summaries.

Numeric laboratory values will be summarized descriptively in SI units, and non-numeric test values will be tabulated when necessary. In addition, line graphs and box-and-whisker plots will be provided for hemoglobin, platelet counts, white blood cells, and neutrophils.

For test results that will be summarized with available normal ranges, the number and percentage of subjects with the laboratory values being low (but never high), normal, high (but never low), and both low and high will be calculated for each test. This shift summary will be produced for each test for the safety population. The denominator for the percentage calculation will use the number of subjects in the baseline category (ie, low, high, normal, missing) as the denominator for the percentage in each of the categories during the treatment period.

For all gradable laboratory parameters shift tables will be presented showing change in CTCAE grade from baseline to worst grade postbaseline for all treatment-emergent laboratory AEs. The number and percentage of subjects with the laboratory values of Grade 1, 2, 3, or 4 will be calculated for each treatment group according to the largest treatment-emergent worsening of laboratory grade. Separate summaries for abnormally high and abnormally low laboratory values will be provided when the laboratory parameter has both high and low grading criteria. The denominator for the percentage calculation will be the number of subjects in the baseline category.

In cases where differentials of hematology parameters are obtained without corresponding absolute count data, efforts will be made to investigate if the conversion to an absolute value will lead to additional abnormalities. This will be discussed with the clinical team regarding appropriate documentation and action.

# 8.4. Vital Signs

Values at each scheduled visit, change, and percentage change from baseline for vital signs, including systolic blood pressure, diastolic blood pressure, pulse, respiratory rate, body temperature, and weight will be summarized descriptively. Change and percentage change from baseline will be calculated using the last nonmissing value before first dose of study drug (Day 1) as the baseline value.

Criteria for clinically notable vital sign abnormalities are defined in Table 6. The abnormal values for subjects exhibiting clinically notable vital sign abnormalities will be listed along with their assigned treatment group. Alert vital signs are defined as an absolute value outside the defined range and percentage change > 25%. The abnormal values for subjects exhibiting alert vital sign abnormalities will be listed.

**Table 6:** Criteria for Clinically Notable Vital Sign Abnormalities

| Parameter                | High Threshold | Low Threshold |
|--------------------------|----------------|---------------|
| Systolic blood pressure  | > 155 mmHg     | < 85 mmHg     |
| Diastolic blood pressure | > 100 mmHg     | < 40 mmHg     |
| Pulse                    | > 100 bpm      | < 45 bpm      |
| Temperature              | > 38°C         | < 35.5°C      |
| Respiratory rate         | > 24/min       | < 8/min       |

## 8.5. Electrocardiograms

Timed triplicate ECGs (separated by 5 minutes) will be conducted at screening and in conjunction with the pre- and postinfusion PK timepoints on C1D1 and C6D1. The baseline ECG measurement will be the average of the 3 nonmissing triplicate ECGs performed preinfusion on C1D1.

Singleton 12-lead ECGs including heart rate, PR, QRS, QT, RR, QTcF, and JTc intervals (where applicable) will be obtained for each subject on Day 1 of every other cycle after Cycle 2 (eg, Cycle 4, Cycle 6, Cycle 8, Cycle 10, etc) during the study. Values at each scheduled visit, change, and percentage change from baseline will be summarized for each ECG parameter. Separate summaries will be provided for triplicate ECGs and singleton 12-lead ECGs.

Criteria for clinically notable ECG abnormalities are defined in Table 7. Subjects exhibiting clinically notable ECG abnormalities will be listed with study visit and assigned treatment group. Abnormal values for subjects with alert ECG values, defined as both the absolute value and the percentage change from baseline being outside normal ranges, will be identified and listed.

Table 7: Criteria for Clinically Notable Electrocardiogram Abnormalities

| Parameter | High Threshold | Low Threshold |
|-----------|----------------|---------------|
| QTcF      | > 460 msec     | < 295 msec    |
| PR        | > 220 msec     | < 75 msec     |
| QRS       | > 120 msec     | < 50 msec     |
| QT        | > 500 msec     | < 300 msec    |
| RR        | > 1330 msec    | < 600 msec    |

OTcF = Fridericia correction.

Electrocardiogram abnormalities, both at baseline and postbaseline visits, will be tabulated by treatment group. Incidences of abnormalities will be listed separately for triplicate and singleton ECGs with study visit, assigned treatment group, and a description of the abnormality.

### 9. INTERIM ANALYSES

There will be no planned, formal interim analyses for the Part 1 dose escalation portion of the study. The review of accrued clinical data will be conducted by Incyte and provided to study investigators via teleconferences at the end of Part 1 of the study. Based on review of the most current safety data, the sponsor (in consultation with the study investigators and using the dose-escalation/de-escalation rules) will determine if and at what dose additional subjects should be treated in the study.

An interim analysis of efficacy will be conducted in Part 2 by applying the Simon 2-stage design. During Stage 1, 9 evaluable subjects treated at the RP2D and schedule will be enrolled, and if no responses (CR or PR) are observed by the Week 16 assessment (at least 2 scans), then the cohort will be discontinued. The probability of early termination for Stage 1 is summarized in Table 8. If at least 1 response (CR or PR) is observed, then 8 additional subjects will be enrolled for Stage 2. In that case, the interim analysis will be conducted with the first 9 evaluable subjects for Stage 1.

[figure not shown]
Per mRECIST v.1.1, the tumor response should be confirmed by a repeat radiographic assessment not less than 4 weeks from the date that the response was first documented. Disease progression will be confirmed by a second tumor assessment in at least 4 weeks and no later than 6 weeks after the first scan indicating PD in clinically stable subjects. The first tumor assessment is conducted at the eighth week. If a CR or PR occurs after an unconfirmed PD in at least 4 weeks but no more than 6 weeks, then the tumor assessment will be counted as a corresponding CR or PR (Table 4).

 Table 8:
 Probability of Early Termination at Stage 1 for Simon 2-Stage Design

| True Response Rate | Probability of Early Termination at Stage 1 |
|--------------------|---|
| 15%                | 23.2%                                       |
| 20%                | 13.4%                                       |
| 25%                | 7.5%  |
| 30%                | 4.0%  |
| 35%                | 2.1%  |

Figure 3 provides the probabilities of early termination with regard to the efficacy analysis of the primary endpoint.

Figure 3: Probabilities of Early Termination for Futility at the End of Simon Stage 1
Based on Various Assumed Rates of Response to a Given Dose Level

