1.3.4.1.1. Modified RECIST

RECIST v1.1 will be adapted to account for the unique tumor response characteristics seen with immunotherapy (Wolchok et al 2009). Immunotherapeutic agents may produce antitumor effects by potentiating endogenous cancer-specific immune responses. The response patterns seen with such an approach may extend beyond the typical time course of responses seen with cytotoxic agents and can manifest a clinical response after an initial increase in tumor burden or even the appearance of new lesions. Standard RECIST may not provide an accurate response assessment of immunotherapeutic agents. Therefore, RECIST v1.1 will be used with the following adaptations:

If radiologic imaging shows initial progressive disease, tumor assessment should be repeated at least 4 weeks, but no later than 6 weeks later in order to confirm disease progression with the option of continuing treatment while awaiting radiologic confirmation of progression.

In subjects who have initial evidence of radiological progression but are clinically stable as defined below, it is at the discretion of the treating physician whether to continue a subject on study drug until repeat imaging is obtained. This clinical judgment decision should be based on the subject's overall clinical condition, including performance status, clinical symptoms, and laboratory data. Subjects may receive treatment while waiting for confirmation of disease progression if they are clinically stable as defined by the following criteria:

- Absence of clinically significant signs and symptoms indicating disease progression.
- No decline in ECOG performance status.
- Absence of rapid progression of disease.
- Absence of progressive tumor at critical anatomical sites (eg, cord compression) requiring urgent alternative medical intervention.

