Part 1 of the study may also include safety expansion cohorts evaluating doses and schedules equivalent to or lower than the highest dose levels determined to be safe and/or doses determined to be pharmacologically active. Each safety expansion cohort will enroll 9 evaluable subjects (up to 36 subjects). If < 3 of 9 evaluable subjects experience a DLT, the cohort will be deemed safe. If more than 1 safety expansion cohort is deemed safe, then the RP2D will be determined in conjunction with the investigators and sponsor based on all available safety, PK, results.

#### 3.4.2. Sample Size in Part 2

Part 2 of the study will further evaluate the safety, tolerability, preliminary efficacy, PK, and pharmacologic activity of the RP2D of INCAGN01876. The sample size for each tumor type will be guided by the Simon 2-stage design (Simon 1989). Let  $P_0 = 5\%$  denote a clinically insignificant response rate for all tumor types. In order to determine whether the target response rate (25%) is likely, an initial number of evaluable subjects (9 subjects) treated at the MTD or PAD and schedule of INCAGN01876 will be enrolled in a cohort (Stage 1). If there is no response for the cohort, it will be concluded that the true response rate is unlikely to be greater than or equal to the target rate, and no more subjects will be enrolled in that tumor type in Stage 2.

In the tumor types in which at least 1 response among the Stage 1 subjects is observed, 8 additional evaluable subjects will be treated in Stage 2 to estimate the response rate. At the end of Stage 2, if  $\leq$  2 subjects have responded among the evaluable subjects, the drug will be declared nonpromising for that tumor type. In other words, after the study is finished, if there is a sufficient number of responses in the 2 stages combined, the study compound is considered promising; otherwise it is considered nonpromising. The detailed calculation is based on a 1-sided Type I error of 0.05 and power of 80% for each of the tumor types. Figure 2 shows the power to reject the null hypothesis for various response rates.

Figure 2: Power and Type I Error for Simon 2-Stage Design for Various Response Rates

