# 7.2. Efficacy Hypotheses

Each Simon 2-stage design will test the null hypothesis that the true ORR is less than or equal to the clinically insignificant response rate 5% against the alternative hypothesis that the true ORR is equal to the target ORR of 25%.

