### 7.4.2. Objective Response Rates and Best Overall Response

A subject is defined as an objective responder if the subject has an overall response of CR or PR at any postbaseline visit before first PD. Objective responders will be assessed based on both RECIST v1.1 and mRECIST v1.1.

Objective response rate is defined as the proportion of subjects with objective responses. Objective response rate will be estimated with 95% CIs overall by cohort-specific tumor type. Confidence intervals will be calculated based on the method for Simon 2-stage CIs of response rates outlined in Koyama and Chen (Koyama and Chen 2008). Subjects who do not have sufficient baseline or on-study response assessment information to be adequately assessed for response status will be included in the denominators in the calculation of ORR.

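### The Stage 1 stop counts only responses by Week 16 while the response rate and final count have no time limit, so Table 8's 7.5% needs no late responses and the 80% power tolerates only about 7.4% late

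*SAP*

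**What the plan says.** SAP section 9 sets the Part 2 futility rule: nine evaluable subjects enter Stage 1 of each cohort, and "if no responses (CR or PR) are observed by the Week 16 assessment (at least 2 scans), then the cohort will be discontinued". SAP section 3.1.3 repeats the limit of 16 weeks and two scans.

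Nothing else in the Simon test has that limit:

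- SAP section 7.4.2 counts as a responder anyone with CR or PR "at any postbaseline visit before first PD".
- SAP section 7.2 takes as null that "the true ORR is less than or equal to the clinically insignificant response rate 5"%, tested "against the alternative hypothesis that the true ORR is equal to the target ORR of 25"%.
- SAP section 3.4.2 declares a tumor type nonpromising with 2 or fewer responders at the end of Stage 2, with no date by which a response must occur. It says the calculation is "based on a 1-sided Type I error of 0.05 and power of 80"% for each tumor type.
- SAP Table 8 gives a 7.5% chance of stopping at Stage 1 when the true rate is 25%.

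The Protocol's version of the stop (sections 4.1.3, 9.4.1.1 and 9.6) has no time limit. Scans continue every 8 weeks after Week 16 (Protocol 7.7.1.1.2), and treatment may run to 26 cycles of 14 days, which is 52 weeks (Protocol 5.2.1). On timing, Protocol 1.3.4.1.1 says of immunotherapy: "The response patterns seen with such an approach may extend beyond the typical time course of responses seen with cytotoxic agents". It adds that a response can follow an initial rise in tumor burden.

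**The concern.** A Stage 1 subject who first responds at Week 24 is a responder for ORR and for the final count of 17, but a zero when the cohort is judged. Table 8 and the power use the same rate for both counts, which is right only if every response has been seen by the Stage 1 look. At stake is the closing of a tumor cohort on nine subjects, with a stated risk of wrongly closing an active one that may be too low.

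There is also a narrower conflict inside SAP section 9. Together with Table 4, it counts a CR or PR found on the scan 4 to 6 weeks after an unconfirmed progression. A progression first seen at Week 16 is rescanned at Weeks 20 to 22, after the cutoff. A response that the SAP itself would count then comes too late to keep the cohort open.

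**Working it through.** **Inputs.** Rates 5% and 25% (SAP 7.2); 9 subjects in Stage 1, stop at 0 responders (SAP 9); 8 more for a total of 17, promising at 3 or more (SAP 3.4.2). The share *L* of responses first seen after Week 16 is in neither document and is assumed. The calculation also assumes that lateness is independent across subjects and that the Week 16 cutoff applies strictly to each of the nine.

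**1. The plan's own figures.** The stop probability is (1 − p)^9. At 15%, 20%, 25%, 30% and 35% it gives 23.2%, 13.4%, 7.5%, 4.0% and 2.1%, which is Table 8.

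Power = P(Bin(17, p) ≥ 3) − (1 − p)^9 × P(Bin(8, p) ≥ 3). At p = 0.25, P(Bin(8) ≥ 3) = 1 − 0.1001 − 0.2670 − 0.3115 = 0.3215, so power = 0.8363 − 0.0751 × 0.3215 = 0.812. The same formula at 5% gives a type I error of 0.0466. The stated design is therefore reproduced with one rate for both counts.

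**2. Late responses.** With p as the any-visit rate:

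- Stop = (1 − p(1 − L))^9.
- Power = P(Bin(17, p) ≥ 3) − Σₖ C(9, k)(Lp)^k (1 − p)^(9−k) P(Bin(8, p) ≥ 3 − k), with k from 0 to 9.

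The sum is the chance that 17 subjects would have given 3 or more responders but the cohort was closed because all k Stage 1 responders were late.

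Example, L = 20%: stop = 0.80^9 = 0.134. The sum is 0.0241 (k = 0) + 0.0285 (k = 1) + 0.0108 (k = 2) + 0.0021 (k ≥ 3) = 0.0655, so power = 0.8363 − 0.0655 = 0.771.

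| Late share L (assumed) | Stop at true 25% | Power at 25% | Type I error at 5% |
|---|---|---|---|
| 0% | 7.5% | 81.2% | 4.7% |
| 5% | 8.7% | 80.4% | 4.6% |
| 10% | 10.1% | 79.5% | 4.5% |
| 20% | 13.4% | 77.1% | 4.2% |
| 30% | 17.7% | 73.8% | 3.9% |

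A simulation of 1,000,000 runs at L = 20% and 30% agrees.

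**3. Threshold.** Setting power to 0.80 gives an early share of 0.926, so the nominal power holds up to L of about 7.4%.

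**4. The other reading of the rates.** Suppose that 5% and 25% are Week 16 rates and the final count stays any-visit. Table 8 then stands, but the any-visit rate under the null becomes 0.05/(1 − L): 5.56%, 6.25% or 7.14% at L = 10%, 20% or 30%. The step 2 formula at those rates gives a type I error of 5.8%, 7.3% or 9.3%, above the 0.05 in SAP 3.4.2 and Protocol 9.3. Only one window for both counts, with the rates defined on it, restores 7.5%, 81.2% and 4.7% together.

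**The case against.** Any futility look needs a data cutoff; the Protocol gives none and the SAP supplies one. Efficacy is secondary (SAP 7.1), all analyses are called exploratory (SAP 3.3), and at 10% late responses power is only half a point below nominal. This limits the weight of the point but does not remove the mismatch.

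The late share has no basis in the documents. The Protocol's remark on timing compares with cytotoxic agents and does not mention Week 16, and Protocol 1.3.4.1.1 places tumor flare in the first few months, which Week 16 largely covers. This stands: the size can only be given as a range.

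The route through initial progression is narrow. Under RECIST v1.1 a response after first progression never counts (SAP 7.4.2.1). Under mRECIST a Week 8 progression is rescanned at Weeks 12 to 14, inside the window. Among the scheduled scans up to the look, only a progression first seen at Week 16 is affected.

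The SAP does not say that the cutoff is strict for each subject. If the look waits for the ninth subject and later responses in subjects enrolled before are counted, the loss is smaller. If the confirmation that SAP section 9 asks for at least 4 weeks later had to fall by Week 16, the loss would be larger. The SAP settles neither.

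**Conclusion.** The mismatch is in the text, and the arithmetic follows from it. On the any-visit reading, which is inferred from the ORR hypotheses and the ORR definition because SAP 3.4.2 names no window, 7.5% is exact only with no response first seen after Week 16. The nominal 80% holds while fewer than about 7.4% of responses are late. For assumed late shares of 10% to 30% under a strict per-subject cutoff, the wrong-stop risk is 10.1% to 17.7% and power is 79.5% to 73.8%.

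A reader might infer more, and the documents do not support it:

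- *That any late response breaks the 80% power.* The exact power is 81.2%, and the margin absorbs a small late share.
- *That the trial is shown to be underpowered.* No late share is given, so the loss is conditional.
- *That an inactive drug is more likely to be called promising.* On the any-visit reading the type I error falls, from 4.7% to 3.9% at 30% late. It rises only if the rates are taken as Week 16 rates with an any-visit final count.

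The correction is worth making because it is cheap and affects whether a cohort is closed.

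**What to change.** (a) In SAP 3.4.2 and 9, keep 5% and 25% as any-visit response rates. State that Table 8 and the 80% power assume that all responses are seen by the Stage 1 look, and add the figures for 10% to 30% late responses. Do not relabel the rates as Week 16 rates while the final count stays any-visit, because of the type I error in step 4 of the working. If Week 16 rates are wanted, apply the same window to the final count of 17.

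(b) In SAP 3.1.3 and 9, count every response in the nine Stage 1 subjects that is known at the decision date. Do not close a cohort with 0 of 9 while any Stage 1 subject has an unconfirmed progression awaiting its 4- to 6-week scan. The stop then agrees with Table 4 and with SAP section 9's own counting rule. This does not recover a response that first appears well after the look; that remaining loss is what the figures in (a) disclose.

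The cost is SAP wording, slightly less favorable stated figures, and a decision up to about 6 weeks later in some cohorts. The planned cohort sizes do not change.
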